8. Describe your plans for monitoring the well-being of subjects including any plans to withdraw subjects from the research if they appear to be unduly distressed.

B. Children

Complete this checklist if the subject population will include children.

1. Select the category of research that you believe this research falls within and provide justification for any associated criteria. If there are different assessments for different groups of children or arms (e.g., placebo vs. drug), include a memo to provide an assessment for each group.

XX Research not involving greater than minimal risk. *(Minimal risk means that the probability and magnitude of harm or discomfort anticipated in the research are not greater in and of themselves than those ordinarily encountered in daily life or during the performance of routine physical or psychological examinations or tests.)*

Research involving greater than minimal risk but presenting the prospect of direct benefit to the individual subjects.

Provide justification for each of the following criteria:

- (1) The risk is justified by the anticipated benefit to the subjects:
- (2) The relation of the anticipated benefit to the risk is at least as favorable to the subjects as that presented by available alternative approaches:

Research involving greater than minimal risk and no prospect of direct benefit to individual subjects, but likely to yield generalizable knowledge about the subject's disorder or condition.

Provide justification for each of the following criteria:

- (1) The risk represents a minor increase over minimal risk:

PROTOCOL TITLE:

- (2) The intervention or procedure presents experiences to subjects that are reasonably commensurate with those inherent in their actual or expected medical, dental, psychological, social, or educational situations:
- (3) The intervention or procedure is likely to yield generalizable knowledge about the subjects' disorder or condition which is of vital importance for the understanding or amelioration of the subjects' disorder or condition

C. Pregnant Women and Fetuses

Complete this checklist if the subject population will include pregnant women and fetuses.

This checklist does not need to be completed if the research is both minimal risk and is not conducted, funded, or otherwise subject to regulation by DHHS, DOD, or EPA.

Provide justification for each of the following:

- 1.** Where scientifically appropriate, preclinical studies, including studies on pregnant animals, and clinical studies, including studies on non-pregnant women, have been conducted and provide data for assessing potential risks to pregnant women and fetuses.

- 1. The risk to the fetus is caused solely by interventions or procedures that hold out the prospect of direct benefit for the woman or the fetus; ***or***, if there is no such prospect of benefit, the risk to the fetus is not greater than minimal and the purpose of the research is the development of important biomedical knowledge which cannot be obtained by any other means.
- 2. Any risk is the least possible for achieving the objectives of the research.

D. Neonates of Uncertain Viability or Nonviable Neonates

Complete this checklist if the subject population will include neonates of uncertain viability.

Provide justification for each of the following:

PROTOCOL TITLE:

1. Where scientifically appropriate, preclinical and clinical studies have been conducted and provide data for assessing potential risks to neonates.
 2. Each individual providing consent is fully informed regarding the reasonably foreseeable impact of the research on the neonate.
 3. Individuals engaged in the research will have no part in determining the viability of a neonate.
-
1. The research holds out the prospect of enhancing the probability of survival of the neonate to the point of viability, and any risk is the least possible for achieving that objective, ***or***, the purpose of the research is the development of important biomedical knowledge which cannot be obtained by other means and there will be no added risk to the neonate resulting from the research

E. Nonviable Neonates

Complete this checklist if the subject population will include nonviable neonates.

Provide justification for each of the following:

1. Where scientifically appropriate, preclinical and clinical studies have been conducted and provide data for assessing potential risks to neonates.
 2. Each individual providing consent is fully informed regarding the reasonably foreseeable impact of the research on the neonate.
 3. Individuals engaged in the research will have no part in determining the viability of a neonate.
-
1. The purpose of the research is the development of important biomedical knowledge that cannot be obtained by other means.

Verify each of the following:

- 5.** Vital functions of the neonate will not be artificially maintained

PROTOCOL TITLE:

True

False

1. The research will not terminate the heartbeat or respiration of the neonate

True

False

2. There will be no added risk to the neonate resulting from the research

True

False

F. Biomedical and Behavioral Research Involving Prisoners

Complete this checklist if the subject population will include prisoners.

Note: Minimal risk for research involving prisoners is the probability and magnitude of physical or psychological harm that is normally encountered in the daily lives, or in the routine medical, dental, or psychological examination of healthy persons.

1. Select and justify which allowable category of research involving prisoners this research falls within:

Study of the possible causes, effects, and processes of incarceration, and of criminal behavior, provided that the study presents no more than minimal risk and no more than inconvenience to the subjects

Study of prisons as institutional structures or of prisoners as incarcerated persons, provided that the study presents no more than minimal risk and no more than inconvenience to the subjects

Research on conditions particularly affecting prisoners as a class (for example, vaccine trials and other research on hepatitis which is much more prevalent in prisons than elsewhere; and research on social and psychological problems such as alcoholism, drug addiction, and sexual assaults)

Research on practices, both innovative and accepted, which have the intent and reasonable probability of improving the health or well-being of the subject

PROTOCOL TITLE:

Epidemiologic studies in which the sole purpose is to describe the prevalence or incidence of a disease by identifying all cases or to study potential risk factor associations for a disease, the research presents no more than Minimal Risk and no more than inconvenience to the subjects, and Prisoners are not a particular focus of the research.

2. Provide justification for each of the following regulatory criteria:

- a)** Any possible advantages accruing to the prisoner through his or her participation in the research, when compared to the general living conditions, medical care, quality of food, amenities and opportunity for earnings in the prison, are not of such a magnitude that his or her ability to weigh the risks of the research against the value of such advantages in the limited choice environment of the prison is impaired
- b)** The risks involved in the research are commensurate with risks that would be accepted by nonprisoner volunteers
- c)** Procedures for the selection of subjects within the prison are fair to all prisoners and immune from arbitrary intervention by prison authorities or prisoners. Unless justification is provided, control subjects must be selected randomly from the group of available prisoners who meet the characteristics needed for that particular research project
- d)** The information is presented in language which is understandable to the subject population
- e)** Adequate assurance exists that parole boards will not take into account a prisoner's participation in the research in making decisions regarding parole, and each prisoner is clearly informed in advance that participation in the research will have no effect on his or her parole
- f)** When appropriate, adequate provision has been made for follow up examination or care after research participation, taking into account the varying lengths of individual prisoners' sentences, and for informing participants of this fact

PROTOCOL TITLE:

III. Medical Devices

Complete this checklist if the research evaluates the safety or effectiveness of a medical device. If more than one medical device is being evaluated, provide the requested information for each.

A. Device Name:

B. Manufacturer:

C. Does the research involve a Significant Risk Device under an IDE?

Yes. Include documentation of the FDA approval of the IDE with your submission.

Acceptable methods of documentation include: (1) FDA letter noting IDE number and approval status; (2) Industry sponsor letter noting IDE number and FDA approval status; or (3) FDA-approved industry sponsor protocol with IDE number noted

No

D. Is the research IDE-exempt?

Yes. Include a FDA letter with your submission noting the determination that the research is IDE-exempt or a letter from the sponsor (or sponsor-investigator) justifying why they believe the research is IDE-exempt*.

No

E. Does the research involve a Non-Significant Risk (NSR) Device?

Yes. Include a FDA letter with your submission noting the determination that the research is NSR or a letter from the sponsor (or sponsor-investigator) justifying why they believe the research is NSR**.

No

* This FDA guidance includes a description for when a device study is exempt from the IDE requirements:

<http://www.fda.gov/downloads/RegulatoryInformation/Guidances/UCM127067.pdf>

**This FDA guidance includes information on how to differentiate between Significant Risk and Non-Significant Risk device studies:

<http://www.fda.gov/downloads/RegulatoryInformation/Guidances/UCM126418.pdf>

PROTOCOL TITLE:

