3.2. Describe blinding, if applicable

Since we are using existing treatment protocols that include different timing intervals of medication administration between methadone and morphine, neither nursing staff nor physicians can be blinded.

4. Inclusion and Exclusion Criteria

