All infants will be monitored for signs of withdrawal using the standard UNM NAS scoring protocol (Attachment: NICU NAS pharmacy protocol). Standard of care at UNM is to treat infants exposed to methadone or heroin in-utero with methadone if they require pharmacologic therapy for NAS, therefore treatment will not be withheld if they choose not to enroll in the study. Standard of care is also to obtain a urine drug screen on all infants with reported exposure to opiates in pregnancy. Enrolled patients will thus undergo routine urine drug screening. The only difference from standard care with regards to the study protocol is the treatment of half of the methadone or heroin exposed infants with morphine. The morphine protocol is proven for safety and efficacy currently in buprenorphine exposed infants at the University of New Mexico, and for all opiate exposed infants in many other institutions.

Randomization will occur by a stratified method in groups of six to ten participants to attempt to control for prenatal exposure (heroin or methadone).

Infants randomized to receive methadone will receive treatment using our standard Methadone Withdrawal Protocol (Attachment: NICU NAS pharmacy protocol).

Infants randomized to receive morphine will receive the drug using the standard Morphine Withdrawal Protocol (Attachment: NICU NAS pharmacy protocol).

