A Data and Safety Monitoring Plan will be developed and will be led by [name] at the University of New Mexico. [name] is an expert in the field of neonatal abstinence syndrome. [name] will monitor the study approximately every 3 months. The report on the Data and Safety Monitoring Plan at Continuing Review will include enrollment and dropout rates, protocol deviations, review of subject symptoms, and preliminary analysis of the primary outcome (newborn length of stay.)

3. Withdrawal of Subjects

- 3.1. *Describe any anticipated circumstances under which subjects may be withdrawn from the research without their consent.*

Infants will be withdrawn if they develop a serious medical comorbidity (eg intubation/ventilation, serious allergic reaction) or require transfer to the neonatal intensive care unit.

- 3.2. *Describe any procedures for orderly termination/safe withdrawal (e.g., tapering of meds, physical exams, laboratory or other tests, etc.).*

This is not applicable to our study. If an infant is withdrawn from the study voluntarily or for the above reasons, they will continue to receive the standard of care therapy but data collection will stop.

- 3.3. *Describe any procedures for partial withdrawal (e.g., from procedures but allowing continued data collection by record review, phone contact, etc.).*

This is not applicable to our study. If an infant is withdrawn from the study voluntarily or for the above reasons, they will continue to receive the standard of care therapy but data collection will stop.

- 3.4. *Describe the disposition of existing data/specimens when a subject withdraws. Describe any restrictions on a subject's ability to withdraw any already gathered data or specimens (e.g., unable to retrieve because it has been stripped of identifiers and no code exists to allow re-linking). (Note: FDA requires that existing data be maintained for studies subject to FDA oversight.)*

If an infant is withdrawn from the study, all of the data related to that individual will be discarded. Data collection will occur upon hospital discharge of the infant, therefore there is not a risk of not being able to retrieve data.

- 3.5. *Describe withdrawal procedures and any limitations in the consent document.*

Please see the consent document for specific information (Attachment 4.)

4. Data Management/Confidentiality

PROTOCOL TITLE:

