- 8.5. *Ensure that the cost section of the consent form reflects the cost that are covered by the sponsor and the costs for which the subjects (or 3rd party payers) are responsible.*

There will be no additional cost to the parents or guardians of test participants other than the routine hospitalization costs for standard of care. All charges related to hospitalization including urine drug screens and therapy with either methadone or morphine are considered to be standard of care and will therefore be billed to the patient’s insurance company (3rd party payer).

23. Compensation

- 8.6. *Describe any plans for compensation or reimbursement for subjects (amounts, methods (e.g., cash card), and payment schedule). Describe why the proposed amount is reasonable and appropriate for the subjects’ time and inconvenience. Credit for payment should be prorated and not be contingent upon the participant completing the entire study. Any amount paid as bonus for completion of the entire study should not be so great that it could unduly induce subjects to remain in the study when they otherwise*

PROTOCOL TITLE:

would have withdrawn. Note: Consult with your department official for reporting requirements associated with cash or merchandise cards distributed to research subjects.

Participants will be compensated with \$20 Walmart merchandise cards.

9. Compensation for Research-Related Injury

- 9.1. *If the research involves more than Minimal Risk to subjects, describe the plan for compensation in the event of research related injury.*
- 9.2. *If subjects are responsible for seeking their own form of care for research-related injury, describe how this will be communicated and what options are available to participants.*

The research uses already existing protocols and therefore does not pose more than minimal risk to subjects, as such we do not anticipate any research related injury.

10. Consent Process

10.1. *Indicate whether you will you be obtaining consent, and if so describe:*

- 10.1.1. *Who will be responsible for obtaining consent and their qualifications/training to do so. Be certain to identify which study team members will obtain consent in Click under Project Contacts.*
- 10.1.2. *Where will the consent process take place and the provisions for privacy.*
- 10.1.3. *The steps that will be taken to minimize the possibility of coercion or undue influence*

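### With no partial withdrawal, a voluntary exit costs the trial length of stay even where the parent would still allow record review, and that loss may be related to outcome and arm

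*Combined protocol and SAP*

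**What the plan says.** In the Withdrawal of Subjects section, the prompt for item 3.3 gives record review as an example of data collection that can continue after partial withdrawal. The answer is that the item does not apply: for those "withdrawn from the study voluntarily or for the above reasons, they will continue to receive the standard of care therapy but data collection will stop". Item 3.2 gets the same answer.

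Item 3.4 adds: "If an infant is withdrawn from the study, all of the data related to that individual will be discarded". It continues: "Data collection will occur upon hospital discharge of the infant, therefore there is not a risk of not being able to retrieve data". That sentence answers a question about removing data already gathered. What matters here is that abstraction happens once, at discharge.

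Other parts of the protocol bear on the point:

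- **Endpoint.** Study Endpoints makes length of hospital stay primary. Study Procedures takes it from the electronic medical record.
- **Timing.** Consent is sought around delivery. The infant is randomised later, when drug treatment is needed (Study Procedures).
- **Blinding.** Because of dosing intervals, "neither nursing staff nor physicians can be blinded" (Study Design, item 3.2). No blinding of parents is described.
- **Standard care.** Study Procedures says: "Standard of care at UNM is to treat infants exposed to methadone or heroin in-utero with methadone if they require pharmacologic therapy for NAS". It describes the trial's only departure from that as "treatment of half of the methadone or heroin exposed infants with morphine". Economic Burden to Subjects, however, says urine screens and "therapy with either methadone or morphine are considered to be standard of care". Drugs or Devices likewise treats both drugs as standard.
- **Analysis.** Data Analysis names no analysis population and no handling of withdrawn infants. The monitoring report covers dropout rates, without saying by arm.
- **Consent.** Item 3.5 refers to the consent document for withdrawal procedures. That document is not among the material reviewed.

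**The concern.** A parent may want to end participation in the assigned treatment without objecting to use of the chart. The plan has no way to record that wish. Voluntary withdrawal is a single step that ends data collection and erases the infant, although the primary endpoint needs only one chart abstraction that was already planned.

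If such exits follow randomisation and depend on how the infant is doing, the infants left are no longer a random sample of their arm. In an open-label trial the dependence may also differ between arms. One route is explicit but conditional: if standard care after withdrawal means methadone, as Study Procedures describes it for this population, leaving would change the drug in the morphine arm and not in the methadone arm.

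The planned regression on pretreatment characteristics would not repair selection that depends on the course of treatment. The pilot is meant to supply effect size and standard deviation for a larger trial, so a distorted estimate would carry forward.

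**Working it through.** **Inputs from the protocol.** A full trial would need 272 infants to detect 3 days (Number of Subjects). Type I error is 0.05 (Data Analysis). About 75% of exposed infants are expected to need treatment (Study Procedures), and the pilot recruits 100.

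**Not given, so assumed.** SD of length of stay, power, sidedness, exit rate, and the relation of exit to stay.

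**Step 1: an SD to work with.** The figure of 272 cannot be reproduced, because neither SD nor power is stated. It can be solved backwards with 136 per arm and a two-sided test:

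SD = 3 / [(1.960 + 0.842) × √(2/136)] = 3 / (2.802 × 0.1213) = 8.83 days at 80% power.

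At 90% power the same calculation gives 7.63 days.

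**Step 2: bias from exits in one arm.** Assume normal stays, no true difference, and a fraction p of one arm leaving. The mean of those retained moves by −p/(1−p) × (mean of leavers − arm mean).

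- *Exit unrelated to stay:* leavers have the arm mean, so the shift is 0.
- *Exits at random from the longer-stay half:* leavers average √(2/π) × SD = 0.798 × SD above the mean.
- *Exactly the longest stays leave (upper bound):* the shift is −SD × φ(z)/(1−p), with φ(z) = 0.1031 at p = 0.05 and 0.1755 at p = 0.10.

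| Pattern of exit (SD 8.83) | p = 0.05 | p = 0.10 |
|---|---|---|
| Unrelated to stay | 0 | 0 |
| Random from longer half | 0.0526 × 0.798 × 8.83 = 0.37 day | 0.1111 × 0.798 × 8.83 = 0.78 day |
| Exactly the longest | 8.83 × 0.1031/0.95 = 0.96 day | 8.83 × 0.1755/0.90 = 1.72 days |

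The last two rows are reductions in that arm's mean. If short stays leave instead, the sizes are the same by symmetry and the sign reverses. With SD 7.63, the four non-zero entries fall in proportion to 0.32, 0.68, 0.83 and 1.49 days.

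**Step 3: cross-check by simulation** (2 million draws). With 10% exits and SD 7.63 to 8.83, a correlation of 0.3 between exit and stay shifts the mean by 0.44 to 0.51 day. A correlation of 0.5 shifts it by 0.74 to 0.86 day. Both are close to the middle row of the table.

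**Step 4: scale.** If the 100 are consented infants, 100 × 0.75 = 75 are randomised, or 37.5 per arm. Then 5–10% of one arm is about two to four infants. The standard error of the difference is 8.83 × √(2/37.5) = 2.0 days. A bias of 0.37 to 0.78 day is 12% to 26% of the 3-day difference, and well inside that standard error.

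**The case against.** The strongest reply has four parts.

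1. **A change of drug need not be a withdrawal.** A reader might infer that a parent who only wants another drug must leave the study. The protocol does not say so. Item 3.1 lists serious comorbidity and NICU transfer as grounds for removal, not drug change. Treating physicians keep medical decision-making, and protocol deviations are to be reported, so a drug change could be logged as a deviation with data collection continuing. This stands: the plan is silent on drug changes.

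2. **The arm-specific motive is not documented.** A reader might also infer that exits would fall mainly on slow-weaning morphine infants and so favour morphine. That needs standard care after withdrawal to mean methadone. Study Procedures supports that reading, but the sentence there reassures families who decline to enrol. Two other sections call both drugs standard, and continuing therapy can mean no change. Potential Benefits to Subjects expects shorter stays on morphine, which weakens any reason to leave that arm. No exit rates by arm or parental preferences are given. This also stands.

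3. **The illustration is small against the noise.** A few infants and under a day of bias, against a standard error of about 2 days, do not overturn a pilot. This stands as to size. But selection bias does not shrink with sample size, and the estimate is intended for planning a larger trial.

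4. **The consent document may already separate the options.** That cannot be checked. If it does, it conflicts with items 3.3 and 3.4, and the texts still need aligning.

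None of this touches the rule itself: voluntary withdrawal ends data collection and discards the infant's data.

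**Conclusion.** The concern holds as a defect in the withdrawal rule. Items 3.3 and 3.4 lose a chart-based primary endpoint for any randomised infant withdrawn voluntarily, including one whose parent would have allowed record review. Withdrawals before randomisation do not raise the problem.

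The loss may be informative and may differ by arm. The documents do not support saying which arm it would favour or by how much. The figures of 0, about 0.4–0.8 day, and at most 1.0–1.7 days rest on an SD back-solved under assumed 80% power and a two-sided test, normal stays, no true difference, and assumed exits of 5–10% from one arm only. The sign depends on who leaves. The change is worth making because it is cheap and removes an avoidable source of selection; the pilot does not fail without it.

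**What to change.** 1. In item 3.3, replace the present answer with two options, one of which is recorded at withdrawal: (a) participation in the assigned treatment stops, but record review to discharge is permitted; (b) full withdrawal, with no further data.
2. Under (a), collect length of stay and the other chart outcomes and analyse the infant in the assigned arm. Under (b), honour the request in full and report the count by arm, with reasons where given.
3. Limit the discard sentence in item 3.4 to (b); otherwise it would undo (a). Conform the repeated wording in item 3.2.
4. Align the consent document with both options.
5. Reconcile Withdrawal of Subjects, Study Procedures, Economic Burden to Subjects, and Drugs or Devices on what standard care means for a withdrawn infant. Which drug that should be is a clinical matter on which this review takes no view.

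The cost is protocol and consent wording, plus a chart abstraction already planned for each infant. The downside is that retained infants who change drug slightly dilute the contrast between arms.
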